10.3.8.2.2. Follow-up after the participant is discharged from the study

The investigator will provide any new or updated relevant information to GSK on a previously reported SAEs/AESIs using a paper/electronic Adverse Events Form and corresponding Expedited Adverse Event Form and/or pregnancy report as applicable. The investigator is obliged to perform or arrange for the conduct of supplemental clinical examinations/tests and/or evaluations to elucidate the nature and/or causality of the SAE/AESI as fully as possible.

10.3.8.2.3. Follow-up of subsequent pregnancies

Maternal participants who become pregnant again while participating in the study will be followed to determine the outcome of the subsequent pregnancy. At the end of the subsequent pregnancy, whether full-term or premature, information on the status of the mother and child will be forwarded to GSK using the electronic pregnancy report and the Adverse Events Form and corresponding Expedited Adverse Event Form if applicable. Generally, the follow-up period does not need to be longer than 6 to 8 weeks after the estimated date of delivery.

Regardless of the reporting period for SAEs in this study, if the pregnancy outcome is an SAE, it should always be reported as such.

Furthermore, if the investigator becomes aware of any SAE occurring as a result of a post-study pregnancy AND it is considered by the investigator to be reasonably related to the study intervention, he/she must report this information to GSK as described in the Section 10.3.10.

10.3.8.3. Updating of SAE, AESI and subsequent pregnancy information after removal of write access to the participant's eCRF

When additional SAE, AESI or subsequent pregnancy information is received after write access to the participant's eCRF is removed, new or updated information should be recorded on the appropriate paper report, with all changes signed and dated by the investigator. The updated report should be faxed to the Study contact for reporting SAEs (refer to the Section 8.3.3.1 or to GSK VCSP department within the defined reporting time frames specified in the Table 18.

10.3.9. Assessment of intensity and toxicity**10.3.9.1. Assessment of intensity**

The intensity of the following solicited AEs will be assessed as described:

Table 27 Intensity scales for solicited events in adults

Adults		
Event	Intensity grade	Parameter
Pain at administration site	0	None
	1	Mild: Any pain neither interfering with nor preventing normal everyday activities.
	2	Moderate: Painful when limb is moved and interferes with every day activities.
	3	Severe: Significant pain at rest. Prevents normal every day activities.
Redness at administration site		Greatest surface diameter in mm
Swelling at administration site		Greatest surface diameter in mm
Temperature*		Record temperature in °C/°F with 1 decimal Temperature will be analyzed in 0.5°C increments from ≥ 38.0°C /100.4°F) Grade 3 fever is defined as > 39.0°C /102.2°F
Headache	0 1 2 3	Normal Mild: Easily tolerated Moderate: Interferes with normal activity Severe: Prevents normal activity
Fatigue		
Nausea		
Vomiting		
Diarrhea		
Abdominal pain		

* Refer to Section 1.3 for the definition of fever and the preferred location for temperature measurement.

The maximum intensity of local injection site redness/swelling will be scored at GSK as follows:

- 0: ≤ 20 mm
- 1: > 20 mm to ≤ 50 mm
- 2: > 50 mm to ≤ 100 mm
- 3: > 100 mm

The investigator will assess the maximum intensity that occurred over the duration of the event for all unsolicited AEs (including SAEs) recorded during the study. The assessment will be based on the investigator's clinical judgment.

The intensity should be assigned to 1 of the following categories:

- 1 (mild) = An AE which is easily tolerated by the participant, causing minimal discomfort and not interfering with everyday activities.
- 2 (moderate) = An AE which is sufficiently discomforting to interfere with normal everyday activities.
- 3 (severe) = An AE which prevents normal, everyday activities (in a young child, such an AE would, for example, prevent attendance at school/kindergarten/a day-care center and would cause the parent(s)/LAR(s) to seek medical advice. In adults/adolescents, such an AE would, for example, prevent attendance at work/school and would necessitate the administration of corrective therapy.)

An AE that is assessed as Grade 3 (severe) should not be confused with an SAE. Grade 3 is a category used for rating the intensity of an event; and both AEs and SAEs can be assessed as Grade 3. An event is defined as 'serious' when it meets 1 of the pre-defined outcomes as described in the Section [10.3.2](#).

10.3.9.2. Assessment of causality

The investigator must assess the relationship between study intervention and the occurrence of each unsolicited AE/SAE using clinical judgment. Where several different interventions were administered, the investigator should specify, when possible, if the unsolicited AE/SAE could be causally related to a specific intervention. When a causal relationship to a specific study intervention cannot be determined, the investigator should indicate the unsolicited AE/SAE to be related to all interventions.

Alternative possible causes, such as the natural history of underlying disease, concomitant therapy, other risk factors, and the temporal relationship of the event to the study intervention will be considered and investigated. The investigator will also consult the IB to assist in making his/her assessment.

Causality should be assessed by the investigator using the following question:

Is there a reasonable possibility that the unsolicited AE may have been caused by the study intervention?

- YES : There is a reasonable possibility that the study intervention contributed to the AE.
- NO : There is no reasonable possibility that the AE is causally related to the administration of the study intervention. There are other, more likely causes and administration of the study intervention is not suspected to have contributed to the AE.

If an event meets the criteria to be determined ‘serious’ (see Section 10.3.2), additional examinations/tests will be performed by the investigator to determine ALL possible contributing factors for each SAE.

Possible contributing factors include:

- Medical history.
- Other medication.
- Protocol-required procedure.
- Other procedure not required by the protocol.
- Lack of efficacy of the study intervention, if applicable.
- An error in study intervention administration.
- Other cause (specify).

There may be situations when an SAE has occurred, and the investigator has minimal information to include in the initial report to GSK. However, it is very important to record an assessment of causality for every event before submitting the Adverse Events Form and corresponding Expedited Adverse Event Form to GSK.

The causality assessment is 1 of the criteria used when determining regulatory reporting requirements. The investigator may change his/her opinion of causality after receiving additional information and update the SAE information accordingly.

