Section 1.3 Schedule of activities, Section 4.1 Overall design, Section 8 Study assessments and procedures, Section 8.1.1 Biological samples, Section 8.1.2 Laboratory assays, Section 8.1.3 Immunological read-outs, Section 10.2.2 Descriptions of the assays to be performed in the study	Updated to remove the collection of hematocrit samples. Table 1, Table 10, Table 13 and Figure 4 have been updated to reflect the changes. Previous Table 15 about hematocrit readout has been deleted to reflect the changes.	Removed due to challenges (mostly due to the COVID-19 pandemic) faced in several countries preventing the samples from reaching the central lab in adequate time for testing. Samples collected until the current Protocol Amendment 1 is approved (unless IEC/IRB allows for immediate implementation of this measure to reduce participant's burden, prior to full Amendment 1 being approved), will be still used for hematocrit analysis if required, as described in Section 10.2.
Section 2.3 Benefit/Risk assessment	Updated to provide details on the current status on expected benefits and risks from receiving the RSV MAT (RSVPreF3) vaccine	Updated to reflect potential changes in the benefit-risk profile.
Section 3 Objectives and Endpoints, Section 9.4.4.1 Safety.	Updated the objectives and endpoints plan and categorized the secondary safety objective as a primary one to assess safety of the infants.	Updated to reflect the change to study's safety assessment plan.
Section 1.2 Schema, Section 4.1 Overall design, Section 6.3.5 – Blinding and unblinding, Section 6.3.5.1 Emergency unblinding, Section 8.2.3.1 Safety evaluation by the Safety Review Team (SRT), Section 8.2.3.2 Independent data monitoring committee (IDMC) evaluation, Section 9.4.3.1 Safety, Section 9.4.4.1 Safety, Section 10.1.6 Dissemination of	Updated to provide details on the blinding status of the study. Table 5 has been updated to reflect the changes and sections impacted by this change have been updated accordingly.	Updated as the study team was unblinded while assessing the safety issue; and also to allow investigators to identify and inform the recipients of the potential risk observed with the RSV MAT vaccination.

Section # and title	Description of change	Brief rationale
clinical study data, Section 10.7.2 Glossary of terms		

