**** Due to the recent safety signal, the study was fully unblinded to ensure the safety monitoring of the participants.***

The laboratory in charge of sample testing will be blinded to the study intervention assignment. Codes will be used to link the participant and study to each sample. There will be no link between the study intervention and the identity of the participant.

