4.2. Primary Endpoint(s) Analyses

4.2.1. Safety

4.2.1.1. Analysis of safety and reactivity planned in the protocol

Safety analyses in maternal participants will include summaries by study group and age category (<18 years; ≥ 18 years; overall) of solicited administration site and systemic events, unsolicited AEs, MAEs, SAEs, MA-RTIs, RSV-associated MA-RTIs, (S)AEs leading to study withdrawal, worsening of pre-existing medical conditions and/or obstetric complications, pregnancy outcomes and pregnancy-related AESIs.

Safety analyses in infant participants will include summaries by study group and gestational age at birth (≥ 37 weeks; <37 weeks; overall) of neonatal AESIs, MAEs, SAEs, (S)AEs leading to study withdrawal, and occurrence of RSV- associated LRTIs, severe LRTIs, RSV-associated hospitalization.

The reactivity analysis will be performed on Solicited Safety Set for maternal participants, and other safety analyses will be performed on the Exposed Sets for both maternal and infant participants.

	Primary Safety Endpoints	Statistical Analysis Methods
Maternal participants	Number and percentage of maternal participants reporting solicited administration site and systemic events during a 7-day (i.e. Day 1 to Day 7 included) follow-up period after dosing.	
The number and percentage with exact 95% CI of maternal participants reporting each solicited administration site event (any grade, each grade,) and solicited systemic event (any, each grade) during the 7-day (7 days post-study intervention, Day 1 included) follow-up period after dosing will be tabulated by maximum intensity per participant for each study group.
 
The number and percentage of maternal participants reporting:
 
 • at least one administration site AE (solicited and unsolicited) • at least one systemic AE (solicited and unsolicited) • any AE 
during the 7-day (7 days post-study intervention, Day 1 included) follow-up period after dosing will be tabulated with exact 95% CI by group.
 
The same computations will be done for Grade 3 solicited and unsolicited AEs, for any unsolicited AEs considered related to study intervention, for any Grade 3 unsolicited AEs considered related to study intervention and for any solicited and unsolicited AEs resulting in a medically attended visit (i.e., MAEs).

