	Number and percentage of maternal participants reporting unsolicited AEs that occur during a 30-day (i.e. Day 1 to Day 30 included) follow-up period after dosing.	
The number and percentage of maternal participants reporting unsolicited AEs within 30 days (30 days post-study intervention, Day 1 included) after dosing with exact 95% CIs will be tabulated by group and by MedDRA preferred term.
 
Similar tabulations will be done for Grade 3 unsolicited AEs, for any causally related unsolicited AEs, for Grade 3 related unsolicited AEs and for MAEs.

CONFIDENTIAL

	Primary Safety Endpoints	Statistical Analysis Methods
	
Number and percentage of maternal participants reporting SAEs, (S)AEs leading to study withdrawal, and MAEs from Day 1 up to 42 days post-delivery.
	
The number and percentage of maternal participants reporting:
 
 • at least one SAE • at least one (S)AE leading to study withdrawal • at least one MAE 
from Day 1 up to 42 days post-delivery with exact 95% CIs will be tabulated by group and by Medical MedDRA preferred term.
 
By participant listings of SAEs, (S)AEs leading to study withdrawal, and MAEs will be prepared.

	
Number and percentage of maternal participants reporting pregnancy outcomes * from Day 1 up to 42 days post-delivery. *These include live birth with no congenital anomalies, live birth with minor congenital anomalies only; live birth with at least one major congenital anomaly, fetal death/still birth (antepartum or intrapartum) with no congenital anomalies, fetal death/still birth (antepartum or intrapartum) with only minor congenital anomalies, fetal death/still birth (antepartum or intrapartum) with at least 1 major congenital anomaly; elective/therapeutic termination with no congenital anomalies; elective/therapeutic termination with only minor congenital anomalies, and elective/therapeutic termination with at least 1 major congenital anomaly.
	
The number and percentage of maternal participants reporting each pregnancy outcome from Day 1 up to 42 days post-delivery will be tabulated with its exact 95% CI by group.
 
By participant listings of adverse pregnancy outcomes will be prepared.

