6.2.3.4. Unsolicited adverse events

Unsolicited AE summaries are including SAEs unless specified otherwise.

Missing severity, relationship with study intervention, and outcome of unsolicited AEs will not be replaced and will appear as 'UNKNOWN' when displayed in a statistical output.

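### After unblinding, the SAP does not say which causality score feeds the 7- and 30-day related-AE tables, so blinded and unblinded judgements can be mixed

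*Protocol*

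**What the plan says.** **Who scores causality.** Protocol 10.3.9.2: "The investigator must assess the relationship between study intervention and the occurrence of each unsolicited AE/SAE using clinical judgment". The answer is yes or no. For serious events the same section adds: "The investigator may change his/her opinion of causality after receiving additional information and update the SAE information accordingly". It gives no time limit and does not say whether learning the allocation counts as additional information. There is no matching sentence for non-serious AEs, and none that locks their score.

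**Who knows the allocation.** Protocol 6.3.5, as amended on 15 March 2022: "Due to the recent safety signal, the study was fully unblinded to ensure the safety monitoring of the participants". The amendment's table of changes gives as one reason "also to allow investigators to identify and inform the recipients of the potential risk observed with the RSV MAT vaccination".

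**Where the score is used.** SAP 4.2.1.1 (Amendment 1, 1 June 2022) repeats the by-group tabulations of the 7-day period "for any unsolicited AEs considered related to study intervention, for any Grade 3 unsolicited AEs considered related to study intervention". For the 30-day period it does so "for any causally related unsolicited AEs, for Grade 3 related unsolicited AEs and for MAEs". SAP 6.2.3.4 adds: "Unsolicited AE summaries are including SAEs unless specified otherwise".

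**Which score is used.** Neither document says. The only SAP rule on the relationship variable (6.2.3.4) is that missing values are shown as unknown. SAP 4.7.1 plans one final analysis once all data to study end are in.

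**The concern.** Relatedness is a judgement, and those who make it now know both the arm and the signal that stopped vaccination. An investigator who learns that a woman received placebo has little reason to leave her event scored as related. One who learns that she received vaccine may be readier to score it so. If the tables take whatever value stands at the end, a single column will hold scores made blind, scores made with allocation known, and scores changed in between. A vaccine-placebo difference in related AEs could then not be told apart from the effect of knowing the allocation. Readers of a trial stopped for safety are likely to look at that column. A score given before unblinding probably exists for many events, but no analysis of it is planned.

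**Working it through.** **1. The plan's own figures.** No figure in the documents bears on this point. The nearest is the chance of seeing at least one AE among 252 vaccinees, 1 − (1 − p)^252. It gives 71.7%, 92.1% and 97.8% at p = 0.5%, 1% and 1.5%, which agrees with the stated 72%, 92% and 98%. The point does not depend on it.

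**2. Timing.**
- Vaccination stopped on 25 February 2022 (Protocol 2.3). With that date as Day 1, Day 30 is 26 March 2022, so every 30-day window had closed by then.
- Unblinding had happened by 15 March 2022; the exact date is not given.
- For SAEs, causality is required at the initial report, and for SAEs and AESIs its review is confirmed within 72 hours (Protocol 10.3.10.1). That is a first score, not a lock: updates to reported SAEs and AESIs may continue after discharge (10.3.8.2.2).
- Many first scores may therefore have been made blind. Later revision is the main route by which allocation could enter, with first scoring of late events a second one.

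**3. Which tables are exposed.** Only the related and Grade 3 related breakdowns for Days 1–7 and 1–30. The SAE and MAE tables to 42 and 180 days, the AESI and pregnancy-outcome tables and all infant tables are not split by relatedness. All-cause counts do not change however causality is rescored.

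**4. Illustration.** Event rates and rescoring are assumptions. Arm sizes are the planned 252 and 126; the number actually enrolled is not stated. The interval is Miettinen–Nurminen, which SAP 4.1.1 names for differences in proportions. Its limits are the values d at which

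(p1 − p2 − d) / √{[q1(1 − q1)/n1 + q2(1 − q2)/n2] · N/(N − 1)} = ±1.96,

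where q1 and q2 are the maximum-likelihood proportions under q1 − q2 = d, and N = n1 + n2.

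Placebo downgrades only. Assume 40% of women have an unsolicited AE and 10% of those are scored related while blind: 252 × 0.40 × 0.10 ≈ 10 and 126 × 0.40 × 0.10 ≈ 5.

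| Related, vaccine v placebo | Difference (points) | 95% CI |
|---|---|---|
| 10/252 v 5/126 (no rescoring) | 0.0 | −5.3 to 4.0 |
| 10/252 v 2/126 | 2.4 | −1.9 to 5.9 |
| 10/252 v 1/126 | 3.2 | −0.6 to 6.5 |
| 10/252 v 0/126 (all five changed) | 4.0 | 1.0 to 7.2 |
| 8/200 v 0/100 (all changed) | 4.0 | 0.2 to 7.7 |
| 6/150 v 0/75 (all changed) | 4.0 | −1.0 to 8.5 |
| 5/126 v 0/63 (all changed) | 4.0 | −1.9 to 9.0 |

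Both arms move. Assume 30% have an AE and about 5% of women are scored related while blind: 13/252 v 6/126, difference 0.4 (−5.3 to 4.8).
- Six of the 63 vaccine-arm unrelated cases upgraded and three of six placebo cases downgraded: 19/252 v 3/126, difference 5.2 (0.2 to 9.5).
- The same fractions at half the size, 9/126 v 1/63: difference 5.6 (−1.8 to 11.8).
- Vaccine upgrades alone: 15 of 63 are needed at the planned size before zero is excluded.

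SAEs only, the one class with written permission to revise. If 3% to 10% of vaccinees have an SAE and 10% to 50% of those are upgraded, 1 to 12 women change. The related rate rises by 1/252 = 0.4 to 12/252 = 4.8 points.

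**5. What the tables will show.** SAP 4.2.1.1 asks for exact intervals per arm, not a difference. For 10/252 that is 1.9% to 7.2%. For 0/126 the upper limit is 1 − 0.025^(1/126) = 2.9%. The two overlap even in the extreme case.

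**The case against.** The best reply is that little depends on these tables. Nothing is tested, all analyses are descriptive, and relatedness is not part of any endpoint definition. The outcomes behind the amendment, preterm birth and neonatal death, are counted whatever their cause. All of that stands, and it limits the point to one set of breakdowns.

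A second reply is that later information may properly change a causality score. Placental pathology (Protocol 10.2.1) and post-mortem findings (10.3.8.2.1) are examples, and tables restricted to the blinded score would lose them. This also stands. It argues for showing both scores, not for leaving the choice unstated.

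Three stronger readings are tempting and are not supported:
- That the SAP says it uses the end-of-study value. It is silent; that value is only the natural default with one final analysis and no other rule.
- That investigators may revise the causality of any AE at will. The written permission covers SAE information and is conditional on additional information. For other AEs there is neither a permission nor a freeze.
- That rescoring would make the arms appear to differ. The illustration needs every placebo event changed at near-planned size, or movement in both arms. No document says how many scores changed.

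**Conclusion.** The point holds as a gap in the SAP. It was amended after unblinding, it still tabulates related AEs by arm, and it does not say whether the blinded or the current score is used. Read by default, the tables mix the two.

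The size is modest and cannot be fixed from the documents. Under the assumed counts, rescoring shifts the between-arm difference by about 1 to 5 points. Whether an interval excludes zero depends on near-complete or two-way rescoring at close to the planned enrolment, which was not necessarily reached. A reader might infer that the primary safety comparison as a whole is compromised. It is not: the all-cause AE, AESI, pregnancy-outcome and infant tables do not use the causality score.

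The conclusion rests on two assumptions: that sites did receive individual allocations, as the amendment intends, and that no rule held outside these documents fixes the value to be used.

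**What to change.** In SAP 4.2.1.1:
- Present the 7- and 30-day related and Grade 3 related tables by the last causality value recorded before that participant's allocation was disclosed to the site. Put events first scored after disclosure in a separate row.
- Present the same tables by the current value alongside.
- List every causality change made after unblinding, by arm, date, and old and new value.

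Expedited reporting continues to use the current value.

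The cost is a paragraph of SAP text, one audit-trail extract and one extra set of tables. Some late events will have no blinded score. The date on which each site learned the allocations must be documented, because the plan does not give it. Protocol 10.1.7 requires changes to source data to be traceable without hiding the original entry, so the earlier scores should be recoverable; confirm that the eCRF audit trail holds them for causality.

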10.3.9.3. Medically attended visits

For each solicited and unsolicited AE the participant experiences, the maternal participant/infant participant’s parent(s)/LAR(s) will be asked if she/the infant participant received medical attention (defined as hospitalization, or an otherwise unscheduled visit to or from medical personnel for any reason, including emergency room visits). This information will be recorded in the in the eCRF.

